## 11. HUMAN SUBJECTS

## 11.1 Participant Consideration

This study is designed to determine the risk factors for decline in kidney function; the incidence of, and risk factors for, impaired neurocognitive development; risk factors for cardiovascular disease; and growth failure.

## 11.2 Clinical Feedback to Participants

The CKiD study investigators recognize the importance of reporting research information to the health care providers of participants. It is essential that investigators report clinically actionable information to the appropriate provider in a timely fashion. A procedure for reporting such information from the Data Coordinating Center to CKiD investigators will be implemented and described in the Manual of Procedures.

## 11.2.1 Transmission of Study Findings and Response Time

As results become available, they will be sent to participant's primary Nephrologist. Permission to forward this information will be obtained during the consent process at the time of study entry. Iohexol-GFR and estimated GFR, based on centrally measured serum creatinine, will be included in the report. Baseline results will be available on Nephron within a timely fashion and will include results of routine laboratory results obtained at the central laboratory. Similar reports will be provided on Nephron or via email to sites after the subsequent study visits. It is important to note that information from tests listed above may be less than the full complement received during tests performed for clinical evaluation.

Feedback from participants' cognitive and developmental assessments will be provided to the families of the participants by the local clinical psychologist in a timely fashion. A procedure for reporting such information is described in the Manual of Procedures.

## 11.2.2 Alert Findings

Participants and their primary Nephrologist will be immediately notified if potentially serious medical problems are identified during any of the examinations. Alerts will be defined as immediate or urgent.

## 11.2.2.1 Immediate Alerts

Immediate alerts are medical emergencies which are encountered or discovered at the time of the study visit such as hypertensive emergencies. These alerts will be evaluated by a physician who will determine the appropriate disposition. Immediate notification of the participant's primary Nephrologist should be accomplished by telephone, prior to the participant leaving the clinic. It is recommended that a follow-up letter documenting information discussed by phone should also be sent to the participant's primary Nephrologist.

## 11.2.2.2 Significantly Abnormal Results

In addition to centrally performed renal panels, clinical sites will perform a local Renal Panel for all study participants. Therefore for certain laboratory tests, such as potassium and glucose, sites will have documented local results; however, the central results will not be known immediately. Clinical sites will obtain central lab results from the Nephron website. On the website, certain significantly abnormal results will be noted with an asterisk. For these significantly abnormal results, it is recommended that the site coordinator notifies the primary Nephrologist within 24 hours after obtaining the results from the Nephron website or their local lab.

## 11.2.2.3 ECHO Alerts and ECHO Incidental Findings

ECHO Alert parameters include findings of congenital disease, vegetation, tumor, pericardial effusion and/or tamponade, left ventricular or atrial thrombus, or cardiomyopathy (hypertrophic/dilated). Local site should screen for "Alert" findings. The local sonographer will enter any of the "alert" findings which they identify during the examination on the Echocardiographic Sonographer's Worksheet. In the event that an alert is found by the local sonographer, the sonographer should contact the site PI. The site PI should notify the study coordinator. The CKID study coordinator and/or PI will then be responsible for calling the patient's referring physician (or physician on record) about the alert. Once the echo is received at the Cardiovascular Imaging Core Research Laboratory (CICRL), the images are also screened for alerts. In instances in which an "alert" parameter is identified and was not recorded on the site sonographer's worksheet, the CICRL cardiologist will review the echo to confirm the alert and the CICRL will provide feedback to the site PI and clinical site sonographer. The site PI will then be responsible for contacting the Primary Nephrologist. All alerts will be reported on the website ECHO Report as "ALERT Found." Otherwise, if no "alert" parameter is identified, then "No Alert" will be indicated on the ECHO Report. Incidental findings that do not fall under an "alert" parameter (such as a patent foramen ovale, or depressed LV function) will also be noted by the CICRL for baseline echos, and will be indicated on the feedback form provided by the CIRCL. It is up to the site coordinator to then notify the PI and referring physician.

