#### 2.3 Cardiovascular Disease in Children with CKD

Cardiovascular disease (CVD) is a major problem in adults with kidney dysfunction, but the incidence and types of CVD present in children with CKD is unknown. The cardiovascular mortality rate reported in children and young adults on chronic dialysis is almost 1000 times higher than in the general population at comparable ages [Parekh 2002]. According to the USRDS 2000 [USRDS 2002] report, 33% of all deaths in children with ESRD were related to cardiovascular causes. In NAPRTCS, 38-78% of children are hypertensive [Fivush 1998, Mitsnefes 2003a] and as many as 60-90% develop hyperlipidemia [Querfeld 1993] and hyperhomocysteinemia [Kang 2002, Lilien 1999, Merouani 2001]. However, it is not clear how these cardiovascular risk factors impact changes in cardiac geometry and function as kidney disease progresses.

Echocardiographic studies in patients with CKD demonstrate identifiable and measurable cardiovascular changes that are associated with renal disease. These include geometric changes which manifest themselves as: left ventricular hypertrophy and increased left atrial size; functional changes in systole and diastole; and vascular changes. Echocardiographic studies of children in all phases of treatment for kidney insufficiency have revealed an increased left ventricular mass (LVM) in 22% of the children with CKD, 30% in those treated with dialysis and in 63% of the transplant group [Johnstone 1996]. An important association has also been noted between LVM and decreasing kidney function in patients with CKD. The clinical sites in the current study

have the capabilities to obtain serial echocardiographic measurements in a standardized fashion by trained technicians using conventional M-mode and 2-D equipment. All participants in this study will undergo baseline echocardiographic assessment to be measured at the second visit with a concurrent GFR, as well as follow up echocardiographic assessments to monitor cardiac function.

This study will systematically assess host risk factors (e.g., genetic susceptibility, age, sex, race, hypertension, malnutrition, lipid abnormalities, proteinuria, inflammation, and anemia) and medical management that may be associated with cardiac dysfunction and echocardiographic changes.

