### 6.4.1.3 Echocardiography

Echocardiographs will performed by be standard M-mode and Doppler echocardiography. The core outcome measurements will include determination of cardiac structure, systolic and diastolic LV function, and vascular (aortic) compliance. Using cardiac and vessel parameters as dependent variables, the contribution of demographic factors, and clinical and laboratory parameters will be assessed. The decision to use M-Mode for LVM calculation is based on recommendations provided in the 4th Report on High Blood Pressure in Children and Adolescents, prepared by NHLBI's National High Blood Pressure Education Program (NHBPEP). Results from the NHBPEP (which will be published in Pediatrics, August 2004) also emphasize the use of this method as a standard procedure to calculate LVM for pediatric centers. The use of a single and relatively simple method for LVM calculation will provide the standardization among multiple participating centers.

The echocardiogram and Doppler studies will be performed in all children at Visit 2 and every four (4) years thereafter. ECHOs will be performed at individual participating sites and recorded on videotapes, but reading and data analyses of ECHO data will be performed by the Cardiovascular Core Imaging Laboratory, Cincinnati Children's Hospital Medical Center (CCHMC). Videotapes/CDs will be sent to the CCHMC with the assigned study ID number as an identifier. The reading center will not have a list of the names of participants that link to the ECHOs and ECHO reports - these will be held by the local clinical centers. Back-up tapes will be stored at the clinical sites. We anticipate that we will be able to achieve standardization and uniformity of ECHOs across sites through training, certification and pre-specified guality control monitoring. CCHMC has experience in coordinating multicenter studies including coordination of ECHOs for the industry-sponsored ramipril study, "The Effect of Ramipril on Ambulatory Blood Pressure and Left Ventricular Mass Index in Children and Adolescents with Hypertension". ECHOs will be performed by certified technicians, and standardized training and certification of designated ECHO technicians at each clinical center will be required.

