# 6.4.3 Outcome Measures

review An Outcomes Adjudication Committee will potential cardiovascular hospitalizations using discharge summary and laboratory reports from these hospitalizations. If the clinical center determines that a cardiovascular event may have occurred during a hospitalization, a discharge summary will be obtained from that hospitalization and forwarded for distribution to the Outcome Adjudication Committee. The committee will then determine outcome status based on the discharge summaries. A cardiovascular outcome will include: sudden cardiac death OR hospitalizations for cardiomyopathy, congestive heart failure, and/or arrhythmias. Patient hospitalizations will also be reviewed for the occurrence of an increase in the dose of diuretics, ACE inhibitors or Angiotensin Receptor Blockers. Because children with CKD are unlikely to develop symptomatic cardiovascular disease, intermediate cardiovascular outcomes found during echocardiographic evaluation also will be evaluated. Specifically, new onset of LVH and LV dysfunction will be reported.

The primary outcomes will be the levels and within-individual changes of cardiovascular markers (e.g., Clinical BP, summary measures of echocardiography). Of particular interest will be the analysis of the association between decline in GFR and risk of progression of CVD as determined by changes in markers of CVD.

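### Section 11.2.2.3 limits the feedback form for echo findings below alert level to baseline echos, so depressed LV function first seen at a follow-up echo has no echo-specific reporting route

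*Protocol*

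**What the plan says.** Section 11.2.2.3 sets two echo-specific routes.

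- **Alert findings** (congenital disease, vegetation, tumor, effusion or tamponade, thrombus, hypertrophic or dilated cardiomyopathy) are screened by the site and again by the core laboratory (CICRL), with no limit to a particular visit. If none is present, "then 'No Alert' will be indicated on the ECHO Report".
- **Findings below alert level**: "such as a patent foramen ovale, or depressed LV function) will also be noted by the CICRL for baseline echos". These go on the CICRL feedback form, and the coordinator must then inform the PI and the referring physician.

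Section 2.3 says which echo is the baseline one: "All participants in this study will undergo baseline echocardiographic assessment to be measured at the second visit with a concurrent GFR". Section 6.4.1.3 sets the repeats: "The echocardiogram and Doppler studies will be performed in all children at Visit 2 and every four (4) years thereafter". It lists "systolic and diastolic LV function" among the core measurements and makes reading central: "reading and data analyses of ECHO data will be performed by the Cardiovascular Core Imaging Laboratory". Section 6.4.3 names the intermediate outcomes: "Specifically, new onset of LVH and LV dysfunction will be reported".

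**The concern.** The second route treats two kinds of finding alike. A patent foramen ovale is there at the first echo or not at all, so reporting it once is enough. LV function can be normal at Visit 2 and depressed at a later echo. The study expects such changes: Section 2.3 says follow-up echos serve to monitor cardiac function, Section 6.4.1.3 hypothesises worsening diastolic function in children who develop LV hypertrophy, and Section 6.4.3 makes new LV dysfunction an outcome.

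The named notification chain therefore operates at the first echo and stops before the echos at which new dysfunction is looked for. A modest patient-safety interest is at stake. The same reading triggers a form and a named recipient at V2, but at V6 it depends on general duties and on whatever the Manual of Procedures adds.

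**Working it through.** There is no plan figure to reproduce. The check is a reading of the sections together and a calendar count.

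**1. Does any section extend the form to follow-up echos?** No. The limit is stated in Section 11.2.2.3, and nothing in Sections 2.3, 5.4, 6.4 or 11.2 removes it.

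**2. Which general routes remain at follow-up?**

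| Section | Duty | Applies at follow-up? | Names echo function? |
|---|---|---|---|
| 11.2 | Report clinically actionable information; procedure left to the Manual | Yes | No |
| 11.2.1 | Send results to the primary nephrologist; comparable reports after later visits | Yes | No; the contents named are GFR and central laboratory results |
| 11.2.2 | Notify at once if a potentially serious problem is found at any examination | Yes | No; depends on that judgement |
| 11.2.2.3 | Alert screening, including cardiomyopathy | Yes | Only if it amounts to an alert |

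The case without a specific rule is thus depressed LV function judged neither an alert nor potentially serious, first seen after baseline. By contrast, Section 11.2.2.2 flags significantly abnormal laboratory results and recommends notification within 24 hours, with no limit to a visit.

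**3. Scheduled echos before RRT, four-year interval (Section 6.4.1.3; visits through V15 in Section 5.4).** V2, V6, V10 and V14 make 4. One is baseline and 4 − 1 = 3 are follow-up, so 3/4 = 75% of the slots fall outside the form.

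**4. Sensitivity to the interval.** Section 8.2.2 gives a different schedule, Visit 2 and then every other year. That would be V2, V4, V6, V8, V10, V12 and V14, which is 7 echos, with 7 − 1 = 6 outside the form and a shorter wait between them. The gap exists on either schedule.

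**5. Echos after RRT (Section 5.4.4).**
- Transplant: echos are described for the even visits, TV2 and TV4. None is listed at TV1a or TV1b, so TV2 is the first post-transplant echo and could be read as a baseline one. That leaves 1 clear follow-up echo (TV4).
- Dialysis: DV1b is called a baseline visit and includes an echo. DV2 to DV5 then give up to 4 follow-up echos.
- Both apply at selected sites only, and the annual post-RRT visits depend on funding (Section 5.4.4.1).

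**6. Time to the next look.** On the four-year schedule, a child with the finding at V6 or V10 is next due a pre-RRT study echo four years later. An irregular visit (Section 5.4.2) can bring that forward if the next consecutive visit is a cardiovascular one.

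All of these count calendar slots. The protocol gives no rate of sub-alert LV dysfunction, so they cannot be turned into a number of children.

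**The case against.** The strongest reply is that follow-up reporting is already required. Section 11.2.1 promises reports after subsequent visits, LV function is a result, and nothing excludes it from those reports. Serious cases are caught at every visit by Section 11.2.2 and by the cardiomyopathy alert, so what remains is by definition less serious. Section 11.2 also states: "A procedure for reporting such information from the Data Coordinating Center to CKiD investigators will be implemented and described in the Manual of Procedures". That Manual is not at hand and may already close the gap. A one-time form for incidental findings is a defensible choice in an observational cohort.

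Most of this stands, and it keeps the point small. What it does not do is restore the specific route. None of the general duties names echo function. A parallel clinical reading cannot be assumed, because Section 6.4.1.3 describes the study echo as elective and outside routine care, and local sites are told to screen for alerts.

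Three stronger readings are tempting, and the protocol supports none of them:
- **That nobody is told.** The general routes apply at every visit.
- **That the ECHO Report would show nothing but the absence of an alert.** Section 11.2.2.3 specifies that entry. It does not say what else the report contains.
- **That new LV dysfunction would be lost as an outcome.** Section 6.4.3 and the central reading are independent of the notification rule.

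**Conclusion.** The point holds as an optional, low-cost improvement. Section 11.2.2.3 states a limit that fits static findings and misfits depressed LV function. The consequence is an uneven notification rule: an echo-specific chain at V2, and only general duties at V6, V10, V14 and post-RRT echos after the first.

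The three-in-four figure assumes the four-year schedule and a child who stays off RRT and under regular follow-up through V14. It should not be read as three quarters of findings, or of children, going unreported. The number affected is unknown. The conclusion also assumes that the Manual of Procedures does not already extend the form; if it does, the protocol sentence only needs to be brought into line with it.

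**What to change.** Amend the incidental-findings sentence in Section 11.2.2.3 so that depressed LV function noted by the CICRL at any study echo, including post-RRT echos, goes on the existing feedback form and is passed on by the coordinator to the PI and referring physician. Apply the same reading standard as at baseline, so that no comparison with the child's earlier echos is needed. Keep static findings, such as a patent foramen ovale, reportable only when first seen.

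The cost is one clause and no new measurement, because LV function is already read at each echo. The downside is a few extra forms and notifications, some for borderline values or for dysfunction the clinician already knows about. No sample size, outcome definition or analysis changes.

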## 11.3 Ethical Issues

The study will be conducted in accordance with Good Clinical Practice as contained in the U.S. Code of Federal Regulations governing the protection of human subjects (Title 21, Part 50) and the obligations of clinical investigators (Title 21, Part 312). This study will also be conducted in accordance with the Declaration of Helsinki.

## 11.3.1 Potential Risks (Study Related Adverse Events)

## 11.3.1.1 GFR

This study is considered to be of minimal to moderate risk because of the safety of the iohexol used for study related procedures. Iohexol (OmnipaqueR) is regularly used in Radiology for intravenous non-ionic contrast for CT studies of the abdomen/chest. The dose of iohexol in radiology is generally 50-200 cc; whereas we will use 5 for the GFR procedure. In a study of approximately 500 children in Scandinavia given iohexol to determine GFR [Stake 1991] using the same small dose specified in our study, iohexol did not cause side effects. In over 8000 studies recently reviewed by Nilsson-Ehle

[Nilsson-Ehle 2001] there were no side effects, even in subjects with a history of iodine hypersensitivity or adverse reactions to x-ray contrast investigations.

At 20 times the dose to be given in this study, iohexol has caused heart rhythm problems in about ½ of 1% of patients. As with any non-radioactive x-ray dye, there is a risk of allergic reaction. Symptoms of a possible allergic reaction include itching, rash, swelling of the face, tongue or throat, sneezing, nasal congestion, a sense of choking or other trouble breathing, wheezing, low blood pressure, dizziness and fainting. The use of iohexol would be contraindicated if a patient had a previous history of difficulty breathing after IV infusion of this agent. Allergic reactions will be treated with antihistamines, epinephrine, and steroids as needed. A study physician will be available during the time of the iohexol infusion.

## 11.3.1.2 Blood Draws

Drawing blood or inserting an IV catheter may cause faintness, inflammation of the vein, pain, bruising, infection or bleeding at the puncture site. The amount of blood drawn at each visit will not exceed the recommendations stated in TITLE 45—Public Welfare and Human Services Part 46—Protection of Human Subjects (i.e. the amount of blood to be collected may not exceed the lesser of 50 ml or 3 ml per kg in an 8 week period and collection may not occur more frequently than 2 times per week.)

## 11.3.1.3 Neurocognitive Tests

Some questions may make a participant feel upset or uncomfortable. Participants will be informed that they do not have to answer any questions that make them feel severely upset or uncomfortable.

## 11.3.1.4 Echocardiogram

There are no confirmed biological effects on patients or instrument operators caused by exposures from present diagnostic ultrasound instruments (echocardiogram). Current data indicate that the benefits to patients of the prudent use of diagnostic ultrasound outweigh any possible risks that may be present.

## 11.3.1.5 Ambulatory Blood Pressure Monitoring

Possible risks associated with use of the ABPM include discomfort, bruising, or injury to the arm when the blood pressure cuff is inflated.

## 11.3.1.6 Vascular Tests

Skin redness or irritation from the heart monitor sticky pads is rare but may occur. Also removing these pads may cause some discomfort similar to taking off a band-aid.

## 11.3.1.7 Cardiac MRI

The magnetic fields and radio waves used during the MRI have not shown to cause any significant side effects. However, feelings of confinement (claustrophobia) and noise made by the magnet during the procedure may be bothersome. Also, because MRI uses powerful magnets, the presence of metal in the body may be a safety hazard. Prior to the exam, you will be asked to complete a standard questionnaire.

## 11.3.1.8 QardioArm (Home Blood Pressure) evice

Possible risks associated with use of the QardioArm device include discomfort, bruising, or injury to the arm when the blood pressure cuff is inflated.

## 11.3.1.9 Grip Strength

There are no confirmed side effects caused by using the grip strength instrument.

## 11.3.1.10 ActiGraph Physical Activity Monitor

There are no confirmed side effects caused by using the ActiGraph monitor.

## 11.3.1.11 Urine Collection Bag

Skin redness or irritation from the adhesive on the collection bag is rare but may occur.

## 11.3.2 Risk/Benefit Assessment

Having an accurate GFR measurement of the child may benefit their clinical care. Current estimations of kidney function from serum creatinine are quite inaccurate, as often as 50% of function can be lost before an increased serum creatinine is documented. A more accurate measure of GFR will allow more accurate assessment of risk for kidney disease progression, safer dosing of nephrotoxic drugs and other drugs cleared by the kidney. We will also be able to institute protective measures, such as more aggressive blood pressure control, at earlier stages of chronic kidney disease.

More complete information about cardiovascular and neurocognitive status will also benefit the clinical care of the child, as risk factors and deficits can be addressed through interventions.

